12.2 Imputation Rules for Missing Prior/Concomitant Medication Dates

Imputation rules for missing or partial medication start/stop dates are defined below:

1. Missing or partial medication start date:
 - a. If only DAY is missing, use the first day of the month.
 - b. If DAY and Month are both missing, use the first day of the year.
 - c. If DAY, Month and Year are all missing, use a date before the first dose date (to impute in practical, use the parent study informed consent date).
2. Missing or partial medication stop date:
 - a. If only DAY is missing, use the last day of the month.
 - b. If DAY and Month are both missing, use the last day of the year.
 - c. If DAY, Month and year are all missing, assign 'continuing' status to stop date (to impute in practical, use the end of study date).

In summary, the prior, concomitant, or post categorization of a medication is described below.

Table 12-2 Prior, Concomitant, and Post Categorization of a Medication

Medication Start Date	Medication Stop Date		
	< First Dose Date of Study Drug	≥ First Dose Date and ≤ End Date of TE Period	> End Date of TE Period
< First dose date of study drug	P	PC	PCA
≥ First dose date and ≤ End date of TE period	-	C	CA
> End date of TE period	-	-	A

P: Prior; C: Concomitant; A: Post

Same imputation rule will be implemented for missing and/or partial dates of non-pharmacological treatment/procedure.

12.3 Imputation Rules for Missing AE dates

Imputation rules for missing or partial AE start date are defined below. If the imputed AE start date is before the informed consent date for the OLS, the AE start date will be imputed using the informed consent date. Ongoing events from the parent study will follow the imputation rule described in the SAP for parent study.

- **If only Day of AE start date is missing:**

- If the full (or partial) AE end date is NOT before the first dose date of the OLS or AE end date is missing, then
 - if AE start Year and Month are equal to the Year and Month of the first dose date of OLS, then impute the AE start Day as the Day of the first dose date of OLS;
 - else impute the AE start day as 1.
- else impute the AE start day as 1.

- **If Day and Month of AE start date are missing:**

- If the full (or partial) AE end date is NOT before the first dose date of the OLS or AE end date is missing, then
 - if AE start Year is equal to the Year of the first dose date of OLS, then impute the AE start Month and Day as the Month and Day of the first dose date of OLS;
 - else impute the AE start Month as January and Day as 1.
- else impute the AE start Month as January and Day as 1.

- **If Year of AE start date is missing:**

If the Year of AE start date is missing or AE start date is completely missing then query site.

- If the full (or partial) AE end date is NOT before the first dose date of the Treatment Period or AE end date is missing, then impute the AE start date as the first dose date of the OLS.
- else impute the AE start date as the informed consent date.

Compare the imputed AE start date with TE period to determine whether the AE is pre-treatment AE, TEAE or post-treatment AE.

Imputation rules for partial AE end date are defined below:

If partial end date, then impute as min (the last day of the month, data cut-off for IA, end of study) if day is missing, or min (Dec, data cut-off for IA, end of study) if month is missing.

12.4 Criteria for Threshold Analysis

Table 12-3 Threshold Analysis Criteria for Laboratory Tests (as applicable)

Parameter	Threshold Analysis	Comments
Clinical Chemistry (LFT)		
ALT	>ULN – ≤3×ULN >3× – ≤5×ULN >5× – ≤8×ULN >8× – ≤20×ULN >20.0×ULN	FDA DILI Guidance Jul 2009.
AST	>ULN – ≤3×ULN >3× – ≤5×ULN >5× – ≤8×ULN >8× – ≤20×ULN >20.0×ULN	FDA DILI Guidance Jul 2009.
ALT or AST	(ALT >ULN – ≤3×ULN) or (AST >ULN – ≤3×ULN) (ALT >3× – ≤5×ULN) or (AST >3× – ≤5×ULN) (ALT >5× – ≤8×ULN) or (AST >5× – ≤8×ULN) (ALT >8× – ≤20×ULN) or (AST >8× – ≤20×ULN) ALT >20×ULN or AST >20×ULN	FDA DILI Guidance
Alkaline Phosphatase	>ULN – ≤1.5×ULN >1.5× – ≤2.5×ULN >2.5× – ≤5×ULN >5× – ≤20×ULN >20×ULN	FDA DILI Guidance Jul 2009.
Total Bilirubin	>ULN – ≤1.5×ULN >1.5× – ≤2×ULN >2× – ≤3×ULN >3× – ≤10×ULN >10×ULN	FDA DILI Guidance Jul 2009.
Direct Bilirubin	>ULN – ≤1.5×ULN >1.5× – ≤2×ULN >2× – ≤3×ULN >3× – ≤10×ULN >10×ULN	FDA DILI Guidance Jul 2009.
Indirect Bilirubin	>ULN – ≤1.5×ULN >1.5× – ≤2×ULN >2× – ≤3×ULN >3× – ≤10×ULN >10×ULN	FDA DILI Guidance Jul 2009.
ALT and Total Bilirubin	ALT >3×ULN and TBILI >2×ULN	FDA DILI Guidance Jul 2009.
AST and Total Bilirubin	AST >3×ULN and TBILI >2×ULN	FDA DILI Guidance Jul 2009.

Table 12-3 Threshold Analysis Criteria for Laboratory Tests (as applicable)

Parameter	Threshold Analysis	Comments
(ALT or AST) and Total Bilirubin	(ALT >3×ULN or AST >3×ULN) and TBILI >2×ULN	FDA DILI Guidance Jul 2009.
GGT	>ULN – ≤ 2.5×ULN >2.5× – ≤ 5.0×ULN >5.0× – ≤ 20.0×ULN >20.0×ULN	CTCAE grade 1-4
Clinical Chemistry (NON-LFT)		
Albumin	<LLN – ≥ 30 g/L <30 – ≥ 20 g/L <20 g/L	CTCAE grade 1-3
Amylase	>ULN – ≤ 1.5×ULN >1.5× – ≤ 2×ULN >2× – ≤ 5×ULN >5×ULN	Criteria based upon CTCAE
Creatinine	>ULN – ≤ 1.5×ULN >1.5× – ≤ 3.0×ULN >3.0× – ≤ 6.0×ULN >6.0×ULN	CTCAE grades 1-4
Lipase	>ULN – ≤ 1.5×ULN >1.5× – ≤ 2×ULN >2× – ≤ 5×ULN >5×ULN	Criteria based upon CTCAE
Total protein	<LLN >ULN	No CTCAE
Creatine Kinase	>ULN – ≤ 2.5×ULN >2.5× – ≤ 5×ULN >5× – ≤ 10×ULN >10×ULN	CTCAE grades 1-4
Hematology		
Hemoglobin	Hgb decreased (anemia) <LLN – ≥ 100 g/L <100 – ≥ 80 g/L < 80 g/L	CTCAE grade 1-3
	Hgb increased >ULN – ≤ 20 g/L above ULN >20 g/L above ULN – ≤ 40 g/L above ULN >40 g/L above ULN	CTCAE grade 1-3
Platelets	Platelet decreased <LLN – ≥ 75.0×10e9 /L <75.0× – ≥ 50.0×10e9 /L <50.0× – ≥ 25.0×10e9 /L <25.0 × 10e9 /L	CTCAE grade 1-4
	Platelet increased >ULN	No CTCAE available

Table 12-3 Threshold Analysis Criteria for Laboratory Tests (as applicable)

Parameter	Threshold Analysis	Comments
Reticulocytes/Erythrocytes (%)	<LLN >ULN	No CTCAE
Coagulation		
Activated partial thromboplastin time (PTT)	>ULN – ≤ 1.5×ULN >1.5× – ≤ 2.5×ULN >2.5×ULN	CTCAE grade 1-3
Prothrombin time (PT) International Normalized Ratio (INR)	>ULN – ≤ 1.5×ULN >1.5× – ≤ 2.5×ULN >2.5×ULN	CTCAE grade 1-3

Table 12-4 Threshold Analysis Criteria for Laboratory Tests (for labeling purpose)

Parameter	Threshold Analysis	Comments
Clinical Chemistry (LFT)		
ALT or AST	>3×ULN >5×ULN >8×ULN	For labeling purpose

Table 12-5 Threshold Analysis Criteria for ECGs

Parameter	Threshold Analysis	Comments
HR	Bradycardia <50 bpm <45 bpm Decrease from baseline ≥10 bpm Decrease from baseline ≥20 bpm <50 bpm and decrease from baseline ≥10 bpm <50 bpm and decrease from baseline ≥20 bpm	Per HV grade 2, 3, plus shift change
	Tachycardia >100 bpm >115 bpm >130 bpm Increase from baseline ≥10 bpm Increase from baseline ≥20 bpm >100 bpm and increase from baseline ≥10 bpm >100 bpm and increase from baseline ≥20 bpm	
PR	≥240 ms ≥300 ms ≥200 ms and increase from baseline ≥40 ms ≥200 ms and increase from baseline ≥100 ms	

Table 12-5 Threshold Analysis Criteria for ECGs

Parameter	Threshold Analysis	Comments
QRS	>110 ms >160 ms Increase from baseline \geq 20 ms Increase from baseline \geq 40 ms	
QTc Borderline Prolonged* Additional	>450 ms and <500ms (Male); >470 ms and <500ms (Female) \geq 500 ms Increase from baseline Increase from baseline >10 ms Increase from baseline >20 ms Increase from baseline >40 ms Increase from baseline >60 ms	To be applied to any kind of QT correction formula.

Note: Based on CPMP 1997 guideline.

Table 12-6 Threshold Analysis Criteria for Vital Signs

Parameter	Threshold Analysis	Comments
Pulse Rate	Same as above in ECG category	
SBP increased	>140 mmHg >160 mmHg >10 mmHg increase from baseline >20 mmHg increase from baseline >140 mmHg & >10 mmHg increase from baseline >140 mmHg & >20 mmHg increase from baseline >160 mmHg & >10 mmHg increase from baseline >160 mmHg & >20 mmHg increase from baseline	809/770 analyses
SBP decrease	<90 mmHg <80 mmHg >10 mmHg decrease from baseline >20 mmHg decrease from baseline <90 mmHg and >10 mmHg decrease from baseline <90 mmHg and >20 mmHg decrease from baseline <80 mmHg and >10 mmHg decrease from baseline <80 mmHg and >20 mmHg decrease from baseline	Per HV grade 1, 3, plus shift change

Table 12-6 Threshold Analysis Criteria for Vital Signs

Parameter	Threshold Analysis	Comments
DBP increased	>90 mmHg >100 mmHg >5 mmHg increase from baseline >10 mmHg increase from baseline	
	>90 mmHg and >5 mmHg increase from baseline >90 mmHg and >10 mmHg increase from baseline >100 mmHg and >5 mmHg increase from baseline >100 mmHg and >10 mmHg increase from baseline	
DBP decreased	<60 mmHg <45 mmHg >5 mmHg decrease from baseline >10 mmHg decrease from baseline	
	<60 mmHg and >5 mmHg decrease from baseline <60 mmHg and >10 mmHg decrease from baseline <45 mmHg and >5 mmHg decrease from baseline <45 mmHg and >10 mmHg decrease from baseline	
Weight	Weight gain ≥5 % increase from baseline ≥10 % increase from baseline ≥ 20% increase from baseline	CTCAE grade 1-3
	Weight loss ≥5 % decrease from baseline ≥10 % decrease from baseline ≥ 20% decrease from baseline	CTCAE grade 1-3

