9.1 Statistical Analysis for Part A

9.1.1 General Considerations

The safety analyses for Part A will be presented for overall with all the subjects pooled together, unless otherwise specified.

The precision standards for reporting safety variables are provided in an internal Biometrics document that specifies the programming rules including the precision for derived variables.

Continuous variables will be summarized using the following descriptive summary statistics: the number of subjects (n), mean, SD, SE, median, minimum value (min), and maximum value (max).

Categorical variables will be summarized using counts and percentages.

Baseline value, unless otherwise specified, for the safety analysis will be the most recent non-missing measurement (scheduled or unscheduled) collected before the first dose of ELX/TEZ/IVA either in a parent study or in Part A of Study 115, as applicable. For assessments collected in duplicate or triplicate, the baseline value will be defined as the average of non-missing values.

Change (absolute change) from baseline will be calculated as Post-baseline value – Baseline value.

Treatment-emergent (TE) Period for Part A will include the time period starting from the date of the first dose of study drug in Part A of this open-label study to 28 days after the last dose of the study drug, or to the completion date of study participation (as defined in Section 9.1.5 of study protocol), whichever occurs first.

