9.1.3.4 Vital Signs

For the vital signs measurements during the TE period for Part A, the observed values and change from baseline values will be summarized at each visit. The following vital signs parameters will be summarized: BMI (kg/m²), weight (kg), systolic and diastolic blood pressure (mm Hg), body temperature (°C), pulse rate (beats per minute), and respiratory rate (breaths per minute).

The number and percentage of subjects meeting at least 1 threshold analysis criterion event during the TE period for Part A will be summarized. The threshold analysis criteria are provided in Section 12.4.

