9.2 Statistical Analysis for Part B

9.2.1 General Considerations

The safety analyses for Part B, unless otherwise specified, will be similar to the safety analyses for Part A. For subjects who depart this study to enroll in another qualified Vertex study and return to this study, details of the associated analysis will be specified in this Section.

In the unlikely scenario that only a few patients roll over into Part B, a descriptive summary may not be performed.

Baseline value, unless otherwise specified, for the safety analysis will be the most recent non-missing measurement (scheduled or unscheduled) collected before the first dose of ELX/TEZ/IVA either in a parent study or in Part A of Study 115, whichever is earlier. For assessments collected in duplicate or triplicate, the baseline value will be defined as the average of non-missing values.

Treatment-emergent (TE) Period for Part B will include the time period starting from the date of the first dose of study drug in Part B of this open-label study to 28 days after the last dose of the study drug, or to the completion date of study participation (as defined in Section 9.1.5 of study protocol), whichever occurs first. For subjects who enroll in another qualified Vertex study before completing this study and resume participation in this study, the TE Period will exclude the time spent in the other study.

Prior and Concomitant Medications

For Part B, medications will be categorized as:

- **Prior medication:** any medication that was administered within the 56 days before the first dose of study drug in Part B of Study 115. For subjects who enroll in another qualified Vertex study and resume participation in this study, any new or changed medication administered after the Departing Visit and prior to the first dose of study drug after resuming participation in this study will also be considered prior medication.
- **Concomitant medication:** medication continued or newly received at, or after, initial dosing of study drug through the end of 115 Part B TE Period.

- **Post-treatment medication:** medication continued or newly received after 115 Part B TE Period.

Study Drug Exposure

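### The weight threshold rows and the weight and BMI change summaries are raw and pooled from age 12 upwards, so adolescent growth can count as graded weight gain and can hide a later weight shortfall

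*SAP*

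**What the plan says.** **Thresholds.** SAP 12.4, Table 12-6, sets three raw weight-gain rows, "Weight gain ≥5 % increase from baseline ≥10 % increase from baseline ≥ 20% increase from baseline", and three mirror-image loss rows. Both sets are labelled CTCAE grade 1-3. No row carries an age limit or a growth adjustment.

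**Counting.** SAP 9.1.3.4 reports the number and percentage of "subjects meeting at least 1 threshold analysis criterion event during the TE period for Part A". Meeting a row once is enough. Gain and loss rows are counted separately and do not net against each other.

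**Continuous summaries.** In the same section, "the observed values and change from baseline values will be summarized at each visit". The parameters begin: "The following vital signs parameters will be summarized: BMI (kg/m²), weight (kg"), so both measures stay in raw units.

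**Pooling.** SAP 9.1.1 has Part A safety results "presented for overall with all the subjects pooled together". The only subgroups in the visible text are for rash (SAP 9.1.3.10). The <18/≥18 split appears in SAP 9.1.2.2 as a baseline characteristic only.

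**Baseline.** For Part A it is the latest value "collected before the first dose of ELX/TEZ/IVA either in a parent study or in Part A of Study 115, as applicable". For Part B it is "either in a parent study or in Part A of Study 115, whichever is earlier", so it is not reset at Part B Day 1. SAP 9.2.3 repeats the Part A safety analyses for Part B.

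**Population and design.** The protocol synopsis admits subjects from age 12, and SAP 7.3 describes a single cohort without randomization.

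**Z-scores.** SAP 12.1 (Derived Variables, item 2) derives age in months for height, BMI and weight z-scores, and SAP 11 cites the CDC growth charts. No visible section defines or summarises a z-score. The heading of SAP 9.1.3.9 has no text under it.

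**The concern.** An adolescent is expected to gain weight over 48 to 144 weeks on any treatment. Measured as raw percent change from a fixed baseline, that gain enters the rows that carry toxicity grades. In the same subject it also offsets a shortfall, so a fall against expected weight may not reach a loss row. BMI adjusts for height only in part, so the pooled BMI change carries growth as well.

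With no control arm and no age split, a reader of these tables cannot tell growth from weight change associated with the drug. The reader also cannot tell whether the adults alone show a pattern. Part B is more exposed than Part A, because its baseline is at least 48 weeks older for a subject who completes Part A.

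**Working it through.** The plan gives no figure to reproduce here: these analyses are descriptive, and the sample size of about 158 is an expected roll-over count. The check asks how much growth would be needed to reach a row.

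**Inputs from the documents**
- Gain and loss rows: 5, 10 and 20% (SAP Table 12-6).
- Treatment: 48 weeks in Part A and 96 in Part B (protocol synopsis).
- Weeks since baseline with no earlier ELX/TEZ/IVA: 48 at Part A Week 48, and 48 + 96 = 144 at Part B Week 96.

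**Assumptions, not in the documents**
- Growth of 2, 5 or 10% of baseline weight a year, linear.
- No parent-study exposure, except where 24 weeks is assumed as a sensitivity case.

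**1. Growth rate at which a gain row is reached.** Rate = row × 52 / weeks.
- 48 weeks: 5 × 52/48 = 5.4; 10 × 52/48 = 10.8; 20 × 52/48 = 21.7% a year.
- 144 weeks: 5 × 52/144 = 1.8; 10 × 52/144 = 3.6; 20 × 52/144 = 7.2% a year.

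Compounding, (1 + row)^(52/weeks) − 1, changes little: 5.4/10.9/21.8 and 1.8/3.5/6.8% a year.

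**2. Growth accrued.** Growth = annual rate × weeks / 52.

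| Assumed rate a year | Part A Week 48 | Gain rows reached | Part B Week 96 | Gain rows reached |
|---|---|---|---|---|
| 2% | 1.8% | none | 5.5% | 5% |
| 5% | 4.6% | none | 13.8% | 5%, 10% |
| 10% | 9.2% | 5% | 27.7% | 5%, 10%, 20% |

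Sensitivity: with an assumed 24 weeks of ELX/TEZ/IVA in the parent study, Part A Week 48 lies 72 weeks from baseline. Accrued growth is then 2.8/6.9/13.8%. Only in that case does the 10% row come within reach in Part A.

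**3. Masking of loss within a subject.** If growth since baseline would have been G, a raw loss of L registers only when the subject is 1 − (1 − L)/(1 + G) below expected weight. For the 5% loss row:
- Part A Week 48, G = 1.8 to 9.2%: 1 − 0.95/1.018 = 6.7% to 1 − 0.95/1.092 = 13.0%.
- Part B Week 96, G = 5.5 to 27.7%: 1 − 0.95/1.055 = 10.0% to 1 − 0.95/1.277 = 25.6%.

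These figures apply to a shortfall present at the late visit. Because one qualifying value is enough, a loss at an early visit, before much growth has accrued, is still counted. That protection is weaker in Part B, where even the first weight lies at least 48 weeks after baseline for a subject who completed Part A.

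**The case against.** The rows apply a named grading scale and do not claim to separate growth from drug effect. No test or decision uses them. The primary endpoint does not name weight or BMI, and protocol 12.3.4.4 does not list either among its vital signs; the SAP adds them. Protocol 12.3.4 promises by-subject listings of all safety data, SAP 12.1 derives age at post-baseline visits for listings where applicable, and protocol 13.1.1.2 has clinically significant worsening recorded as an AE whatever the threshold rows show. Part B may not be summarised at all: "In the unlikely scenario that only a few patients roll over into Part B, a descriptive summary may not be performed".

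All of this stands, and it keeps the stakes low. It does not alter the summary tables. A listing does not correct a pooled percentage, SAP 9.1.3.4 names no weight listing, and the SAP itself calls the few-subjects scenario unlikely.

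A reader might go further and infer that the sponsor left out a z-score analysis. The documents do not support that. The age derivation and the CDC reference suggest one was intended, and a summary may have stood under the empty heading of SAP 9.1.3.9. Table 12-6 and the SAP 9.1.3.4 summaries would remain raw and pooled either way.

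A reader might also infer that growth alone reaches the 10% row in Part A, or that adolescent weight loss would go unseen. Without assumed parent-study exposure the first fails over the range used here (9.2% at most). The second overlooks the rule that one qualifying value is enough.

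**Conclusion.** The point holds as a minor one. Nothing in the visible plan separates growth from other weight change, so growth can be counted as graded weight gain and can hide a later shortfall within a subject. The pooled weight and BMI changes carry growth too.

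The direction follows from the documents; the size does not. Over the assumed range the effect in Part A is confined to the 5% row, and only at the fast end (5.4% a year or more). By Part B Week 96 it runs from the 5% row to the 20% row. These figures assume linear growth at a constant rate and no parent-study exposure. They illustrate what one growing subject could show. They do not estimate how many subjects would be misread.

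**What to change.** 1. In Parts A and B, present the Table 12-6 weight rows and the weight and BMI change-from-baseline summaries separately for <18 and ≥18 years at parent-study screening, the stratum already in SAP 9.1.2.2. This keeps most growth out of the adult rows. It does not separate growth from drug effect within <18, and some of that stratum will turn 18 during the study.

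2. For growth itself, define weight and BMI z-scores in SAP 9.1.3.4, stating the reference and its age range. Use the age-in-months derivation and the CDC reference already in the SAP. Summarise values and change from baseline by visit for subjects within that range, and carry this into SAP 9.2.3. If such a summary already exists outside the visible text, cite it in both sections.

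**Cost.** A SAP amendment, one derivation and a few descriptive tables, some with small adolescent counts. No new data are needed. Weight is collected in both parts. Under protocol 11.2.4, subjects who consent to Part A on or before their 21st birthday have height collected through the first visit after it.

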12.5 Adverse Events of Special Interest

Table 12-7 MedDRA Preferred Terms for Event of Special Interest	
Adverse event of special interest	MedDRA preferred terms
Elevated transaminases	Alanine aminotransferase abnormal, Alanine aminotransferase increased, Aspartate aminotransferase abnormal, Aspartate aminotransferase increased, Transaminases abnormal, Transaminases increased, Liver function test abnormal, Liver function test increased, Hypertransaminasaemia, Hepatic enzyme abnormal, Hepatic enzyme increased
Rash	Rash, Rash erythematous, Rash macular, Rash maculo-papular, Rash maculovesicular, Rash vesicular, Rash pruritic, Rash follicular, Rash pustular, Nodular rash, Drug eruption, Fixed eruption, Urticaria, Urticaria papular, Urticaria vesiculosa, Urticarial dermatitis, Rash morbilliform, Rash papular, Rash papulosquamous, Rash rubelliform, Rash scarlatiniform, Drug hypersensitivity, Type IV hypersensitivity reaction, Dermatitis, Dermatitis atopic, Epidermolysis, Skin toxicity, Dermatitis allergic, Dermatitis exfoliative, Dermatitis exfoliative generalised, Erythema multiforme, Exfoliative rash, Mucocutaneous rash, Acute generalised exanthematous pustulosis, Cutaneous vasculitis, Urticarial vasculitis, Dermatitis bullous, Drug reaction with eosinophilia and systemic symptoms, Epidermal necrosis, Oculomucocutaneous syndrome, Skin exfoliation, Skin necrosis, Stevens-Johnson syndrome, Toxic epidermal necrolysis, Toxic skin eruption, Perioral dermatitis, Vasculitic rash, Immune-mediated dermatitis, Penile rash, SJS-TEN overlap, Erythrodermic atopic dermatitis, Scrotal dermatitis, Anal Rash, Generalised bullous fixed drug eruption

Note: The preferred terms listed in the table is based on the MedDRA version applicable at the time of finalization of the SAP. If the MedDRA version is upgraded at the time of the final analysis, the corresponding preferred terms based on the upgraded version will be used in the analysis of adverse events of special interest.
